3.7 Stopping Guidance and Interim Analysis

Timing of the interim analysis. The Data and Safety Monitoring Committee will meet to review the interim efficacy data when 34 treatment failures have occurred. This represents approximately 40% of the anticipated 84 events expected in the trial based on the assumed median failure times used in the primary analysis sample size calculation (median 10 weeks in the stopping group, and 20 weeks in the adalimumab group). Timing the interim at 40% of events was chosen as a trade-off between having sufficient events to make interim efficacy, futility and safety analyses informative, and

timeliness with respect to the trial informing patient care in the event of stopping under one of the guidelines.

The DSMC will make one of the following recommendations:

- Continue the trial without modifications
- Continue the trial with study modifications
- Stop enrollment in the trial because of efficacy
- Stop enrollment in the trial because of futility
- Stop enrollment in the trial because of safety concerns

The DSMC will take into consideration (a) safety, (b) efficacy, (c) clinical importance, and (d) validity to make a final decision regarding stopping guidance implementation. If patient safety is not at risk, then consideration of secondary outcomes may outweigh the need for immediate reporting of the primary outcomes.

Efficacy. An unmasked interim analysis will be conducted when 34 treatment failures have occurred (the primary endpoint) to determine whether or not there is sufficient evidence to answer the primary aim and justify stopping additional enrollments.

We propose a group sequential boundary for judging the statistical significance of the primary outcome, allowing for the interim analysis. We propose a Kim-DeMets flexible alpha spending approach, implemented in the *gsDesign* package in R, with power function $\alpha^*(t^*)^\theta$, where $\theta = 1.75$ (θ chosen so that the two-sided *P*-value to stop the trial for efficacy is exactly 0.01 when 40% of events have occurred).³⁷ The detectable HR at the interim analysis is 2.4 at the original, 88% power. A nominal two-sided *P*-value of 0.044 at the final analysis will account for the proposed interim analysis under a group sequential design. The Appendix includes details of the parameters and output from R's *gsDesign* package.

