13.1 Estimates of interim efficacy calculations

Here, we have included the details of the interim efficacy calculations. Calculations were implemented using R's `gsDesign` package. They assume a single interim efficacy analysis takes place when 40% of the treatment failures (n=34 of an anticipated 83 total failures) occur. The calculations further assume that the interim analysis will spend 0.01 of the two-sided 0.05 alpha, using a Kim-DeMets power spending function.

```
>
> #-----
> # ADJUST trial
> # Interim analysis planning
> #
> # [name]. June 8, 2023
> #
> # the assumptions and approach
> # follow the vignette online at:
> # https://cran.r-project.org/web/packages/gsDesign/vignettes/gsSurvBasicExamples.html
> #-----
>
> #-----
> # preamble
> #-----
> rm(list=ls())
> library(gsDesign)
>
>
> #-----
> # fixed design calculation
> #
> # Note: this calculation uses
> # a slightly different approach
> # from the original trial's sample
> # size calculation. All approaches
> # suggest the trial will require
> # 81-83 treatment failures to have
> # 88% power to detect a HR=2.0
> # The original calculation assumed
> # patients would be enrolled
> # and followed until exactly 48 weeks,
> # the timing of the primary endpoint. This
> # mimics the actual design.
```

```

> # gsDesign assumes that patients
> # will enrolled over a period (we assume 1 week)
> # and will be followed for a minimum of 48 weeks
> # but may continue to be followed past
> # that point. There is also a slightly difference
> # in how the package handles losses to follow-up
> # compared with the original calculation.
> # the slight difference in approach results in
> # the same total number of events required
> # with slightly different total sample sizes (118 vs 122)
> # however, this nuance would not change
> # the interim calculations and adjustment
> # which is based on number of events, not total patients
> # -----
>
> # Median Adalimumab time-to-event
> # assume time to event in STOP/placebo is 10
> # and time to event in continue is 20
> median_fail0 <- 20
> # Exponential dropout rate per unit of time (assume 10% per year)
> #  $\exp(-0.0022 \times 48 \text{ weeks}) = 0.9$ 
> eta <- 0.0022
>
> # Hypothesized experimental/control hazard ratio (alternate hypothesis)
> # The original sample size calculation design effect is HR = 2. (or 0.5)
> hr <- 0.5
> # Null hazard ratio (1 for superiority, >1 for non-inferiority)
> hr0 <- 1
> # Type I error (1-sided)
> alpha <- .025

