> # Type II error (1-power)
> # set at 12% (88% power, per original sample size calculation)
> beta <- 0.12
>
> # accrual assumptions
> # Enrollment period duration (only one)
> # assume all patients are enrolled simultaneously, over 1 week
> R <- c(1)
> # Follow-up duration of last patient enrolled
> minfup <- 48
> # Study duration (weeks) / 4 years = 192 weeks
> # if set to NULL, then nSurv solves for total study duration
> # required for the last patient to complete minfup (48 wks)
> T <- 49
>
> # Relative enrollment rates during above periods (constant)
> gamma <- c(1)
> # Randomization ratio, experimental/control
> ratio <- 1
>

```

```

> #-----
> # calculate the fixed design,
> # using gsDesign's nSurv()
> #-----
> d_fixed <- nSurv(
+   lambdaC = log(2) / median_fail0,
+   hr = hr,
+   hr0 = hr0,
+   eta = eta,
+   gamma = gamma,
+   R = R,
+   T = T,
+   minfup = minfup,
+   ratio = 1,
+   alpha = alpha,
+   beta = beta
+ )
>
> d_fixed
Fixed design, two-arm trial with time-to-event
outcome (Lachin and Foulkes, 1986).
Solving for: Accrual rate
Hazard ratio           H1/H0=0.5/1
Study duration:          T=49
Accrual duration:          1
Min. end-of-study follow-up: minfup=48
Expected events (total, H1):    81.0482
Expected sample size (total): 122.2344
Accrual rates:
  Stratum 1
0-1 122.2344
Control event rates (H1):
  Stratum 1
0-Inf 0.0347
Censoring rates:
  Stratum 1
0-Inf 0.0022
Power:           100*(1-beta)=88%
Type I error (1-sided): 100*alpha=2.5%
Equal randomization: ratio=1
>
>
> #-----
> # Allow for a single interim analysis
> #-----
>
> # Number of analyses (interim + final)
> k <- 2
> # Timing of interim analyses (k-1 increasing numbers >0 and <1).

```

```

> # Proportion of final events at each interim.
> timing <- c(0.4)
> # Efficacy bound spending function.
> # We use Lan-DeMets Power spending function .
> # No parameter required for this spending function.
> # with power parameter set to 1.75, which corresponds to
> # a nominal two-sided P-value of 0.01 at the interim with 40% of events
> sfu <- sfPower # use sfLDOF approximating O'Brien-Fleming bound
> sfupar <- 1.75 # use NULL if O'Brien-Fleming
> # Futility bound spending function -- NOT used, set test.type = 1 below
> sfl <- sfLDOF
> # Futility bound spending parameter specification -- NONE set test.type = 1 below
> sflpar <- 0 # NULL
>
> # Generate design
> d_seq <- gsSurv(
+   test.type = 1,
+   k = k, timing = timing, R = R, gamma = gamma, eta = eta,

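### SAP 3.7 gives 88% interim power at a hazard ratio of 2.4, but 2.4 is only the boundary value (power about 43–49%); its 84 expected events are required events from a 20 vs 40 week run

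*SAP*

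**What the plan says.** SAP 3.7 schedules one interim efficacy look at 34 treatment failures, with stopping at two-sided P = 0.01 and a final nominal level of 0.044. It makes two statements about that look.

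- Power: "The detectable HR at the interim analysis is 2.4 at the original, 88% power".
- Timing: 34 failures are "approximately 40% of the anticipated 84 events expected in the trial based on the assumed median failure times", which it gives as 10 weeks for stopping and 20 weeks for adalimumab. The introduction to SAP 13.1 gives "n=34 of an anticipated 83 total failures".

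SAP 13.1 prints the script (June 2023) and its output. The code comments say "assume time to event in STOP/placebo is 10" and 20 for continuing. The code itself has "median_fail0 <- 20" under the comment "Median Adalimumab time-to-event", then "lambdaC = log(2) / median_fail0" for the control hazard, with an experimental/control hazard ratio of 0.5. The output lists a boundary Z of 2.57 at 34 events, an efficacy-boundary hazard ratio of 0.410 at 33.24 events, and crossing probabilities under the design alternative of 0.2857 (interim), 0.5943 (final) and 0.880 (total). Its closing summary calls the 84 events required.

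**The concern.** A hazard ratio that is detectable with 88% power at a look should lead to crossing at that look 88 times in 100. An observed ratio sitting on the boundary is a different quantity: if the true ratio equals it, the trial crosses about half the time. The 88% sentence is the only interim power figure in the text of 3.7, and 3.7 justifies timing the look at 40% of events by its being informative. A reader would take 2.4 as reliably detectable at 34 failures when it is close to a coin toss.

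The timing statement has a related fault. It attaches a required event count to a scenario of 10 versus 20 weeks that the script did not run, so the appendix appears to confirm the planned scenario when it does not.

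**Working it through.** **Inputs.** 34 interim events, two-sided P = 0.01 (z = 2.576), 118 patients allocated 1:1, 48 weeks of follow-up, 10% loss (SAP 2.4.1, 3.3.1, 3.7); dropout 0.0022 per week, control median 20, ratio 0.5, 88% power (SAP 13.1). Failure and dropout are taken as exponential.

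**1. Where 2.4 comes from.** Boundary ratio = exp(2Z/√d).
- At 33.24 events: exp(2 × 2.57/√33.24) = 2.44 = 1/0.410, the printed value.
- At 34 events, with z = 2.576: 2.42.

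**2. Interim power at a true ratio HR.** Schoenfeld: Φ(½√34 · ln HR − 2.576). Freedman: Φ(√34 · (HR − 1)/(HR + 1) − 2.576).

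The log-rank column is an unstratified simulation stopped at the 34th failure: 59 per arm, continuing-arm median 20 weeks, dropout as in the script, 20,000 runs per cell. Accrual was 1 week or 150 weeks. The 150 weeks is an assumption: Protocol 5.5 anticipates 3–4 patients per month, so 118 patients take about 128 to 170 weeks.

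| True HR | Schoenfeld | Log-rank simulation (1 / 150 weeks) | Freedman |
|---|---|---|---|
| 2.0 | 29% | 27.0 / 27.9% | 26% |
| 2.4 | 49% | 44.9 / 45.5% | 43% |
| 3.62 | 88% | 82.9 / 83.1% | 77% |
| 4.0 | 93% | 88.8 / 89.3% | 82% |

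A simpler simulation (simultaneous entry, no dropout, 8,000 runs) gave 25.3% at 2.0 and 43.7% at 2.4. The SAP's own 28.6% at 2.0 agrees with the Schoenfeld value.

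The ratio giving 88% interim power is exp(2 × (2.576 + 1.175)/√34) = 3.62 by Schoenfeld, about 4.0 by simulation and 4.6 by Freedman. Turned round, 88% at a ratio of 2.4 needs 4 × (2.576 + 1.175)²/(ln 2.4)² = 73.4, so 74 events. Using alpha 0.01 or 0.05, one- or two-sided, no Schoenfeld or Freedman variant pairs 88% with 2.4; the nearest is 2.63.

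**3. Which medians the script used.** Control median 20 with experimental/control ratio 0.5 gives an experimental median of 20/0.5 = 40 weeks. At 20 vs 40 the printed output reproduces: 81.05 events from 122.23 patients, 83.11 from 125.34, and 33.24 events at week 12.75. At 10 vs 20, 122.23 patients would give 105.2 events, and 33.24 events would arrive at week 6.6.

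**4. Events expected at 10 vs 20 weeks from 118 patients.** Event probability = λ/(λ + η) × [1 − exp(−48(λ + η))], with λ = ln 2/median.
- Script dropout: 59 × (0.938 + 0.780) = 101.4.
- No loss: 59 × (0.964 + 0.811) = 104.7.
- If the 10% lost contribute nothing: 53.1 × (0.964 + 0.811) = 94.2.

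So 34 is 34/84 = 40% of the required events, but 34/101.4 = 34% of the expected events (32% to 36%).

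**5. Effect on the levels.** Solving the script's fixed design gives 80.4 required events at 10 vs 20 and 81.0 at 20 vs 40, so the requirement hardly moves. The 0.01 and 0.044 levels are calibrated to 34 of 84 events. With 101.4 final events the information fraction is 0.335 and the correlation of the two statistics is √0.335 = 0.58. The same two levels then give overall two-sided alpha of 0.0506 (0.0503 at 94 events, 0.0507 at 105).

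**6. The comparison of 118 with 122 patients.** The 3.3.1 formula with T = 48 gives 105.8/0.9 = 117.6 at 10 vs 20, which reproduces the planned 118, but 131.8/0.9 = 146.5 at 20 vs 40. The comment sets 118 from one pair of medians against 122 from the other.

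**The case against.** The strongest reply is that nothing operational depends on the sentence. The look has taken place, and the DSMC stopped enrollment on 14 February 2024. The correct figures (0.2857, 0.410, 84 required) stand in the appendix to which 3.7 refers. The appendix also says that the trial needs 81–83 failures, and that the interim adjustment depends on events and not patients. The word expected probably comes from a line of the script's own fixed-design output. All of this stands, and it limits the point to the record.

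One might also read 88% as power over both looks. That does not rescue the sentence: in the output, 88% over both looks belongs to a ratio of 2.0.

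The replacement figures are approximations as well. The planned test is a permutation test of a Cox coefficient adjusted for country and antimetabolite use, with failures recorded at discrete visits. Any restated power should therefore name its method.

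A reader might infer three stronger things.
- *That the script error undermines the boundary or the stopping decision.* It does not. Required events barely depend on the medians, and the change in alpha is trivial.
- *That type I error is exactly preserved.* That holds only at 84 final events. The SAP fixes the sample size and analyses when patients complete 12 months; no look is scheduled at 84.
- *That the trial could not detect 2.4.* The shortfall concerns stopping at the interim. Had 84 failures been analysed, Schoenfeld power at 2.4 would have been Φ(½√84 × ln 2.4 − 2.01) = 98%.

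**Conclusion.** The power sentence is wrong as written. A ratio of 2.4 is the value at the boundary, with interim power of about 43–49% (Schoenfeld 49%, log-rank simulation 44–46%, Freedman 43%). At 2.0 it is about 26–29%, or 25% in the simplest simulation. An 88% chance at 34 failures needs about 3.6 (Schoenfeld) to 4.0 (simulation), and more by Freedman.

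The 84 events are a requirement for a ratio of 2.0, taken from a 20 versus 40 week run. About 101 (94 to 105) would be expected from 118 patients under the medians that 3.7 names. These figures assume exponential failure and dropout, and the simulations an unstratified log-rank test.

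The 34-failure trigger and the interim result are not in question. The correction is worth making because it is nearly free and this section supports a result on which enrollment was stopped.

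**What to change.** Issue a dated correction note, recorded in the revision history as made after the interim, as version 5 was.

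- (a) Replace the power sentence with: *An observed hazard ratio of about 2.4 just crosses the interim boundary. Approximate interim power (Schoenfeld / unstratified log-rank simulation) is 29% / 27% at 2.0 and 49% / 45% at 2.4; 88% needs a ratio of about 3.6 to 4.0.*
- (b) Relabel 84 in 3.7, and 83 in 13.1, as events required for a ratio of 2.0 at 88% power. State that about 101 (94 to 105) are expected at 10 vs 20 weeks. Add that the 0.01 and 0.044 levels are calibrated to 84 events, and that with about 101 final events overall two-sided alpha would be about 0.0506.
- (c) Note that the June 2023 script ran 20 vs 40 weeks, so its comparison of 118 with 122 patients is not like with like, and that required events (about 80–81) hardly change.

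Leave the June 2023 output as printed. No rerun is needed, and no replacement patient number in the comment: at equal medians the two methods differ by about 24 patients (146.5 − 122.2), a gap that a new number would leave unexplained.

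The cost is a short note and a less favourable stated interim power. Trigger, levels, patients and data do not change.

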3.8 Final Analyses

All analyses will be completed when all patients complete their last visit at 12 months.

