4.2 SCIENTIFIC RATIONALE FOR STUDY DESIGN

Justification for placebo treatment: As both patients and those assessing outcomes could introduce bias, complete masking of the treatment is ideal for this study. This concern is especially pertinent for the pediatric population, since it is difficult to prevent young patients from discussing their treatment with their physician. Our primary outcome is time to treatment failure, where treatment failure is defined as a recurrence of ocular inflammation (≥ 2 -step increase in AC cell observed at 2 consecutive visits at least 7 days apart; $>0.5+$ AC cell for ≥ 28 days; $\geq 3+$ AC cell observed at a single visit; or $>0.5+$ vitreous haze, active retinal/choroidal lesions, or macular edema at a single visit) and/or a recurrence of joint inflammation that is persistent and severe enough to necessitate unmasking to manage the arthritis recurrence. While an attempt will be made to ensure the grading of ocular inflammation is as standardized as possible, complete removal of subjectivity in inflammation grading is impossible. Furthermore, we plan to assess adverse events and quality of life as secondary outcomes, which rely on patient self-report. Given that self-report is involved in both the primary and secondary outcome assessments, masking of subjects is also necessary to remove any potential bias in assessing the outcomes for our study.

Justification for superiority: There is clinical utility in determining if one treatment plan is more effective for reducing the risk of recurrence of ocular inflammation. The findings of this trial could provide justification for either stopping adalimumab or continuing adalimumab for long-term management of JIA-associated uveitis and CAU, which are chronic conditions. Therefore, a superiority trial design is warranted.

Potential problems with placebo treatment: We hypothesize that stopping adalimumab will result in a shorter time to treatment failure and higher uveitis recurrence rates compared to continuing adalimumab. In anticipation of this possibility, we have allowed for patients to restart adalimumab or be treated per best medical judgement for the remainder of the study period. The primary analysis will be intent-to-treat, but we will also collect clinical outcome data at Month 12 to assess whether the initial strategy of stopping treatment results in worse outcomes compared to the initial strategy of continuing therapy.

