10.1.12.5 TRIAL SAFETY

A masked medical monitor at the CC has been appointed to evaluate the safety of the trial. All serious adverse events experienced by enrolled patients will be reported to the medical monitor in a timely manner, as defined in section 8.3.6. The medical monitor will determine expectedness of the patient's treatment and the reported event. The medical monitor will report his findings to the relevant entities defined in section 8.3.6.

The NEI's appointed DSMC will also review serious adverse events and general trial data on a 6-month basis, or as deemed necessary. Progress reports will be prepared for all scheduled DSMC meetings. An interim analysis will be performed and presented to the DSMC by the trial's unmasked biostatistician when approximately 40% of the trial's anticipated events have occurred. Whether or not to continue the trial will be based on this interim analysis. See **SAP section 3.7** for details on stopping.

On February 14th, 2024 the DSMC met, stopped enrollment and provided the following guidance for patients still completing follow-up in the trial:

- Patients should be told by the study investigator the results regarding efficacy of the continued administration of adalimumab for preventing recurrence of uveitis or arthritis.
- Patients are encouraged to remain in their assigned treatment group and complete follow-up, per protocol.
- Patients in active follow-up who have not yet been unmasked to their treatment assignment can be asked if they want to know their current treatment assignment.
- Patients receiving placebo may opt to discontinue their injections.

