3.3 Sample Size Estimation

3.3.1 Primary Calculation

A sample size of 118 subjects (59 in each group) provides 88% power to detect a hazard ratio of 2.0 for the time to treatment failure comparing the group randomized to discontinue adalimumab to the group randomized to continue using adalimumab, assuming a median time until treatment failure of 10 weeks in the group that discontinues adalimumab (Arm 1) and of 20 weeks in the group that continues on adalimumab (Arm 2), an equal allocation between groups, and a 10% total loss to follow-up.

For sample size planning, we use the approximate formula given in Friedman et al (2010) for the number in each group:

$$N = \frac{(Z_\alpha + Z_\beta)^2 (\phi(\lambda_C) + \phi(\lambda_I))}{(\lambda_I - \lambda_C)^2}$$

Where λ denotes the rate in the intervention arm (λ_I) and control arm (λ_c), $\phi(\lambda) = \lambda^2 / 1 - e^{-\lambda T}$ at censoring time T , and Z_α, Z_β are quantiles from the standard normal distribution at power (1- β) and significance level α .

In a retrospective study by our group of JIA-associated uveitis patients on immunomodulatory therapies (antimetabolites, cyclosporine, TNF- α inhibitors, or combination therapy), 37% of patients attempted to stop treatment after achieving corticosteroid-sparing control of inflammation.²³ Of patients who stopped TNF- α inhibitors, nearly 50% experienced a recurrence of inflammation within 100 days after stopping treatment. Approximately 80% of patients had a recurrence of ocular inflammation within one year after stopping treatment.

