In a clinical trial of JIA-associated uveitis patients with active inflammation on a stable dose of antimetabolite, 114 patients were randomized to adalimumab or placebo biweekly subcutaneous injections and followed for up to 18 months.²⁶ The mean duration of sustained inactive disease was 179.3 ± 16.9 days in the adalimumab treatment group (vs. 14.5 ± 23.9 days in the placebo group). An open label long-term follow-up study of non-infectious adult uveitis patients treated with adalimumab demonstrated that, among patients with inactive disease who entered the study, over 90% of patients still had inactive disease at week 54.²⁷ At 78 weeks, 74% still had inactive disease.²⁸ Given the available evidence on disease recurrence for patients on long-term adalimumab treatment, we can expect a lower recurrence rate and longer time to treatment failure in patients continuing on adalimumab compared to those discontinuing treatment. While these studies suggest that most uveitis patients on adalimumab remain inflammation-free greater than one year, we have conservatively estimated 20 weeks to be the median time to treatment failure among patients randomized to continue adalimumab treatment.

Thus, 118 patients total (59 per group), provides 88% power to detect a hazard ratio of 2.0 for the time to treatment failure, assuming a 10% loss to follow-up. We assume an alpha of 0.05 (two sided). Adjusting for country in our analyses is assumed to give us even greater power. A power table is provided in Table 4 below, varying the median time until treatment failure (in weeks).

Table 4: Total Sample Size Based on Median Time to Treatment Failure for Stopping vs. Continuing Adalimumab

		80% Power	90% Power
Stopping Treatment Versus Continuing Treatment	8 weeks vs 16 weeks	92	124
	10 weeks vs 20 weeks	96	126
	12 weeks vs 24 weeks	98	130

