Unmasking active patients at such an interim point compromises patient and personnel efforts already initiated towards the trial, as well as their study data. Enrolled patients will remain in the study. Enrollment, however, shall stop in an effort to disseminate study results sooner so that patients considering discontinuation of adalimumab can make better informed decisions about future treatment. The DSMC may reconsider the decision regarding the protocol for patients who have not completed their follow-up if/when stopping guideline criteria are met.

For the Statistical Analysis Plan, adverse event reporting will be descriptive in nature. Serious adverse events (SAEs) are reported directly to the medical monitor within 24 hours of the time the study site learns of them, and the medical monitor will subsequently pass this information on to the DSMC Chair. The medical monitor will receive notification of the event, the timing of the event, a medical narrative from the study site, the site location, and the patient identification number. The statistician will report the study treatment assignment to the DSMC Chair if deemed necessary by the DSMC. If use of either intervention clearly results in an unacceptable increase in the risk of treatment failures, then the study will be stopped.

In the event of that the DSMC stops the trial early, for any reason, the final analysis will be conducted on the available data.

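### The full-follow-up analyses combine visits before and after the 14 February 2024 disclosure, and the SAP has no rule to separate them

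*SAP*

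**What the plan says.** **Plan for an efficacy stop (SAP 3.7).** Enrollment stops, enrolled patients continue under the existing protocol, and unmasking follows treatment failure. Their outcomes count in the primary and secondary analyses. The section adds: "Unmasking active patients at such an interim point compromises patient and personnel efforts already initiated towards the trial, as well as their study data". It lets the DSMC reconsider the arrangements for patients still in follow-up.

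**What was put in place (Protocol 10.1.12.5).** On 14 February 2024 the DSMC stopped enrollment. Investigators were to tell patients the efficacy results. Patients still masked "can be asked if they want to know their current treatment assignment". Those on placebo could opt to stop injections. Patients were encouraged to stay in their assigned group and complete follow-up.

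**What SAP version 5 changed.** Its revision history says the changes followed the interim analysis and unmasking. SAP 3.1.1 records the decision to publish the interim primary analysis at once and adds longitudinal models on interim data for visual acuity, JADAS, drug levels and antibody levels. SAP 3.1.3 adds time to initial and to sustained control after failure.

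**What it left.** SAP 3.8: "All analyses will be completed when all patients complete their last visit at 12 months". SAP 3.7 ends by saying that, after any early stop, the final analysis uses whatever data are available, and gives no date. Censoring is defined at 12 months (2.3.1), at 6 months (3.1.1) and at loss to follow-up (3.4). None of these refers to disclosure or elective unmasking.

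**The concern.** Protocol 4.2 justifies the placebo on the ground that "complete removal of subjectivity in inflammation grading is impossible" and because self-report enters both primary and secondary outcomes. After disclosure, the investigator and patient know which strategy did better, and some may know the arm. Three things can then change:

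- Grading of anterior chamber cells near a failure threshold.
- The arthritis component of failure. It requires a recurrence severe enough to need unmasking, which has no clear meaning for a patient who has already chosen to be unmasked.
- Adherence. Permission to stop injections applies to one arm only.

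Quality of life is the most exposed outcome. It is self-reported, and it is not among the outcomes given an interim-data analysis. A reader of the final report could not tell how far a 12-month result depends on visits made after the answer was known.

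**Working it through.** **1. The plan's own figures reproduce.** Inputs from SAP 3.3.1: "A sample size of 118 subjects (59 in each group) provides 88% power to detect a hazard ratio of 2.0", "assuming a median time until treatment failure of 10 weeks in the group that discontinues adalimumab (Arm 1) and of 20 weeks" when treatment continues, two-sided alpha 0.05, 10% loss. With T = 48 weeks:

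- λ(stop) = ln 2/10 = 0.0693 and λ(continue) = ln 2/20 = 0.0347.
- φ(λ) = λ²/(1 − e^(−λT)), giving 0.00498 and 0.00148.
- N per arm = (1.960 + 1.175)² × (0.00498 + 0.00148)/(0.0347)² = 52.9.
- Total with 10% loss = 2 × 52.9/0.9 = 117.6, so 118.

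The interim boundary in SAP 3.7 also reproduces: 0.025 × 0.4^1.75 = 0.00503 one-sided, 0.0101 two-sided, with a final two-sided level of 0.0440. The point below concerns a missing data rule and does not depend on these figures.

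**2. Which results have an analysis on interim data.**

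| Result | Interim-data analysis in SAP v5 | Uses follow-up after 14 Feb 2024 | Rule at disclosure |
|---|---|---|---|
| Time to treatment failure | Yes (3.1.1) | Yes (3.7, 3.8) | None |
| Visual acuity, JADAS, antibody levels | Yes (3.1.1) | Yes | None |
| Proportion failing by 6 and 12 months | No | Yes | None |
| Quality-of-life scores | No | Yes | None |
| Aim 3 control at months 6 and 12 | No | Yes | None |
| Time to sustained control | Only patients past month 12 | Yes, all patients later (3.1.3) | None |

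That the later analyses combine both periods is inferred from SAP 3.7 and 3.8 and the all-randomized population in SAP 4.1; no sentence says so outright.

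**3. How many patients.** The documents give no count. I simulated 118 patients entering at a constant rate, allocated 1:1, with exponential failure recorded at the next scheduled visit (weeks 4, 8, 12, 16, 24, 32, 40, 48) and no dropout. I stopped at the 34th recorded failure and counted event-free patients short of week 48. Accrual rates and the large-effect medians (150 weeks continuing, 14 stopping) are assumptions.

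| Accrual per month | Medians, weeks (continue/stop) | Month of 34th failure | Enrolled | Event-free, in follow-up |
|---|---|---|---|---|
| 1.5 | 20/10 | 29.6 | 44.4 | 7.3 |
| 1.5 | 150/14 | 45.5 | 68.2 | 11.3 |
| 1.75 | 20/10 | 26.0 | 45.5 | 8.5 |
| 1.75 | 150/14 | 39.5 | 69.2 | 13.1 |
| 3.5 | 20/10 | 15.0 | 52.7 | 17.1 |
| 3.5 | 150/14 | 22.0 | 77.2 | 26.2 |

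From the anticipated start of March 2020 (Protocol 1.1) to 14 February 2024 is about 47 months. The 3.5 rows match the 3 to 4 per month anticipated in Protocol 5.5 but not this calendar. The closest row is 1.5 per month with a large effect, about 11 patients. Under the design medians, slowing accrual to 1.0 per month moves the 34th failure to month 42 and leaves about 5.

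**4. Direction of bias.** Patients inside their 48-week (11.1-month) window at the stop number about 1.5 × 11.1 = 16.6 or 1.75 × 11.1 = 19.4. Against the enrolled totals above, that is 24% (16.6/68.2) to 43% (19.4/45.5). An illustration with 118 patients, design medians, true hazard ratio 2.0 and no dropout gives:

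| Share in window | Censored at the date | Pooled, placebo hazard halves after disclosure | Pooled, declared failures +50% on placebo, −20% on adalimumab |
|---|---|---|---|
| 25% | 2.01–2.03 | 1.95 to 1.89 | 2.07 to 2.11 |
| 40% | 2.00–2.02 | 1.91 to 1.84 | 2.09 to 2.17 |

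Within each pooled cell, the first value has 50% of patients changing and the second 100%. With no change in behaviour the pooled value is 2.02 to 2.04. Censoring keeps about 92 to 97 of about 105 events.

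**The case against.** The strongest reply is that version 5 already contains a data cut. The primary outcome, four longitudinal outcomes and time to regaining control are analysed on data available at the interim, before patients were told. SAP 6.2.2 also has the database archived for each DSMC report. This stands, and it confines the point to the later analyses.

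SAP 3.7 also considers a patient who is unmasked and on placebo, expects no return to therapy without recurrence, and lets the DSMC reconsider. That authorises the change in conduct but supplies no analysis rule. The per-protocol set drops patients who missed 20% or more of study medication, which may catch some who stopped placebo. It removes whole patients rather than post-disclosure time, and does nothing about knowledge of the result.

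Censoring has dangers of its own. Every treatment failure is unmasked by protocol, so censoring each patient at unmasking would delete the post-failure data on which Aim 3 is defined. Elective unmasking is the patient's choice, so censoring at that date may be informative. Replacing intent-to-treat full follow-up as the main analysis would be a change made after unmasking. These objections stand and shape the fix.

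Finally, analyses after each Aim's primary are descriptive (SAP 3.5). That lowers the stakes without removing them: estimates and intervals will still be read.

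**Conclusion.** The gap is real and limited. Protocol 10.1.12.5 departs from the conduct planned in SAP 3.7, SAP 3.7 itself says unmasking at that point compromises the data, and version 5 neither separates the two periods nor reconciles the available-data rule in 3.7 with the complete-follow-up rule in 3.8.

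A reader might infer more than the documents support:

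- That the efficacy finding is compromised. It rests on the interim analysis, and the revision history calls the effect much larger than anticipated.
- That most patients learned their arm. Uptake of unmasking is not reported.
- That the Interim Masking Decision Form supplies disclosure dates. Protocol 1.3 says when it is completed, not what dates it records.
- That 17 to 26 patients are affected. Those counts need accrual that does not fit the calendar.

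The size is about 7 to 13 event-free patients under assumed accrual of 1.5 to 1.75 per month (9 to 13 at 1.75, 7 to 11 at 1.5). The illustrative pooled hazard ratio runs from 1.84 to 2.17 around a true 2.0. The behaviour changes are assumed and the true effect differs from the design value, so this shows that direction is unpredictable; it does not estimate the actual bias.

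**What to change.** Add to SAP 3.8:

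1. State that the interim analysis, with its data cut date, is the primary efficacy result. Reconcile SAP 3.7 and 3.8 with each other and with Protocol 10.1.12.5.
2. Add an analysis of time to treatment failure and of the longitudinal outcomes, administratively censored for everyone at 14 February 2024 rather than at self-chosen unmasking dates. Report it beside the full-follow-up intent-to-treat analysis.
3. For fixed-time outcomes and Aim 3, keep post-failure data. Add a sensitivity analysis limited to assessments made before that date, or split by whether the patient was still masked at disclosure.

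Label these as specified after the interim, as version 5 does for its other additions. The cost is a few sentences, one more set of models and somewhat fewer events in the censored analysis. Which of the two analyses leads is a judgement; reporting both is what protects the later results.
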